11.5 Removal of Subjects from Therapy or Assessments

Although the importance of completing the entire clinical study will be explained to the subjects, any subject is free to discontinue his/her participation in the study at any time and for whatever reason, specified or unspecified, and without any prejudice. No constraints are to be imposed on the subject, and when appropriate, a subject may be treated with other conventional therapy when clinically indicated once the subject is no longer in the study. Investigators or the sponsor can also withdraw subjects from the clinical study if deemed to be necessary.

Unless medically urgent, investigators are required to contact the Medical Monitor to discuss patients that are being considered for withdrawal from study drug treatment or from the study.

A subject may be withdrawn from the study treatment at any time for the following reasons:

- At the discretion of the investigator or the sponsor for safety, behavioral, compliance, or administrative reasons.
- Occurrence of AEs, including laboratory abnormalities, not compatible with the continuation of subject participation in the study, in the investigator's opinion, or unacceptable to the subject to continue, including but not limited to the following:
 - Serious immediate-type allergic manifestations including anaphylactic reaction;

- Serious new or worsening of asthma, or newly diagnosed asthma considered related to study drug administration;
- Diagnosis of a malignancy (except curatively treated in situ cervical carcinoma, squamous cell carcinoma [Bowen's disease] or basal cell carcinoma);
- Opportunistic infections such as but not limited to active TB and other infections whose nature or course suggest an immune-compromised or immune-suppressed status;
- Any serious infection or any severe infection requiring treatment with parenteral antibiotics or oral antibiotics/antivirals/antifungals for > 2 weeks considered related to study drug administration; or
- Confirmed COVID-19 infection (at least a temporary discontinuation is required, while suspected COVID-19 may be acceptable see Section 11.5.2).
- ALT or AST > 3 x ULN and TBL > 2 x ULN or INR > 1.5
- Pregnancy, for which discontinuation of study drug is mandated.
- Use of non-permitted systemic concurrent therapy (discussed and agreed upon with the investigator and medical monitor).

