4.7 Handling of Missing Data

Missing data of the following dichotomous efficacy endpoints:

- Proportion of subjects with an improvement of WI NRS ≥ 4 from baseline at Week 12
- Proportion of subjects with an improvement of WI NRS ≥ 3 from baseline at Week 12
- Proportion of subjects with an improvement of WI NRS ≥ 4 from baseline at Week 4

- Proportion of subjects with an improvement of SD NRS ≥ 4 from baseline at Week 12
- Proportion of subjects with an improvement of WI NRS ≥ 3 from baseline at Week 4
- Proportion of subjects with an improvement of SD NRS ≥ 4 from baseline at Week 4
- Proportion of subjects with an improvement of WI NRS ≥ 4 from baseline at Week 1

will be imputed using multiple imputations (MI) under missing at random (MAR) assumption for the primary/main analysis. Dichotomous endpoints will be calculated from the underlying imputed variable (i.e., weekly averages of WI NRS and SD NRS, as applicable).

For the sensitivity analyses of the primary endpoint, missing data will be imputed using a copy reference (CR) approach under missing not at random (MNAR) assumption (dichotomous endpoints will be calculated from the underlying imputed variable) and as “Non-responder”; moreover a Tipping Point analysis under MNAR assumption will be carried out (see [Appendix C](#) for details about Multiple Imputation and Tipping Point analysis).

[figure not shown]
Multiple imputation will be based on data collected up to Week 12. A further sensitivity analysis based on MI using all data collected up to Week 20 may be performed.

Similarly, sensitivity analyses will be performed by imputing missing data using a CR approach under MNAR assumption and as “Non-responder” for the key secondary efficacy endpoints based on WI NRS and SD NRS.

[figure not shown]
Subjects who took rescue therapies or discontinued treatment due to lack of efficacy or AE/death related to study drug will be considered as treatment failures in the endpoints defined for Estimands 1 to 6 (see section [5](#)). The values of the variable of interest collected after the use of rescue therapies or treatment discontinuation due to lack of efficacy or AE/death related to study drug will be set to the worst possible value and subject’s binary response will be imputed as “Non-responder” prior to conducting the MI and Tipping Point analysis.

Missing data of the following dichotomous efficacy endpoint:

CCI

A large black rectangular box redacting content.

CCI

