Estimand 3: In adult hemodialysis patients with chronic kidney disease and associated moderate to severe pruritus, 2 nemolizumab dosing schedules ^[1] compared to placebo by the difference in proportions of responders where response is defined as an improvement from baseline of WI NRS ≥ 4 at Week 4 without use of	
Treatment Conditions: initial dose of nemolizumab (60 mg) or placebo at baseline, then nemolizumab (30 mg or 60 mg) or placebo Q4W at Weeks 4 and 8 via subcutaneous injection.
 
Population: adult hemodialysis patients with chronic kidney disease and associated moderate to severe pruritus (will be estimated in the Intent-to-Treat analysis set).
 
Variable: a binary composite response where: Responder is defined as an improvement ≥ 4 in WI NRS from baseline at Week 4 without use of rescue therapies and without treatment discontinuation due to lack of efficacy or AE/death related to study drug. Non-responder is defined as an improvement < 4 in WI NRS from baseline at Week 4 or use of rescue therapies or treatment discontinuation due to lack of efficacy or AE/death related to study drug.

Efficacy Estimand Description	Estimand Attributes
rescue therapies and without treatment discontinuation due to lack of efficacy or AE/death related to study drug	
Strategies for Intercurrent Events: A composite strategy was chosen for the use of rescue therapies and treatment discontinuation due to lack of efficacy or AE/death related to study drug; in case of use of rescue therapies or treatment discontinuation due to lack of efficacy or AE/death related to study drug, subjects will be considered as treatment failures in the binary composite response. In the case of treatment discontinuation for any other reason, a treatment policy strategy will be used and observed after discontinuation data (if available) will be used.

	
Summary measure: treatment difference of nemolizumab versus placebo in proportions of responders

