- Subjects who discontinued treatment due to lack of efficacy or AE/death related to study drug before achieving onset of effect on pruritus from baseline will be censored and the date of treatment discontinuation will be used as censoring date.
- Subjects who discontinued treatment for any other reason, did not take rescue therapies and did not achieve onset of effect on pruritus from baseline during the study will be censored and date of end of participation will be used as censoring date.
- Subjects who did not take rescue therapies, did not discontinue treatment and did not achieve onset of effect on pruritus from baseline during the study will be censored and date of end of participation will be used as censoring date.

In case of occurrence of both intake of rescue therapy and treatment discontinuation due to lack of efficacy or AE/death related to study drug, the earlier date will be used for censoring purposes.

[figure not shown]
The following rules will be applied:

1 st Intercurrent Event	2 nd Intercurrent Event	Censoring Rule
Intake of rescue therapies	Treatment discontinuation due to lack of efficacy or AE/death related to study drug	Subjects will be censored and the date of decision to put subject under rescue therapies will be used as censoring date
Intake of rescue therapies	Treatment discontinuation for any other reason	Subjects will be censored and the date of decision to put subject under rescue therapies will be used as censoring date
Treatment discontinuation due to lack of efficacy or AE/death related to study drug	Intake of rescue therapies	Subjects will be censored and the date of treatment discontinuation will be used as censoring date
Treatment discontinuation for any other reason	Intake of rescue therapies	Subjects will be censored and the date of decision to put subject under rescue therapies will be used as censoring date

In order to investigate the impact of rescue medication intake and treatment discontinuation, cumulative incidence functions for competing-risks data will be presented and compared between treatment groups by using Gray's test.

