Proportion of subjects with an improvement WI NRS ≥ 4 from baseline at Week 1 will be analyzed in the ITT Set, using the Cochran-Mantel-Haenszel (CMH) test stratified by analysis center. The strata-adjusted difference in proportions of responders with 97.5% CI, pooled CMH test p-value will be derived as described in section [9.1.1](#). Subjects who took rescue therapies will be considered as treatment failures, efficacy data collected after the use of rescue therapies will be set to the worst possible value and subject's binary response will be imputed as "Non-responder". Treatment discontinuation due to lack of efficacy, AE/death related to study drug or any other reason is not a factor at this early timepoint since the second administration is not due until Week 4. Missing subject's binary response will be imputed using MI under MAR assumption (dichotomous endpoints will be calculated from the underlying imputed variable). See [Appendix C](#) for details about Multiple Imputation.

[figure not shown]
CCI

CCI

CCI

11 Immunogenicity Analyses

The immunogenicity endpoint is nemolizumab immunogenicity in adult hemodialysis subjects with moderate to severe pruritus.

Anti-drug antibodies assessments using a validated electro-chemiluminescence immunoassay (ECLIA) (screening, confirmatory, titer, Nab) and incidence of positive ADA results (absolute occurrence, percent of subject, and treatment-related ADA) will be summarized by visit and by treatment group. A treatment-related ADA is defined when at baseline, the screening or confirmatory ADA result is negative, and the post-baseline confirmatory ADA result is positive. A corresponding listing will be provided.

Summaries will be based on the Safety Set. Subjects will be summarized according to their actual treatment group.

12 Safety Analysis

Safety assessments/measurements will be conducted for all subjects at the screening visit (upon signing of the ICF) and at every subsequent visit as described in schedule of assessments in [Appendix A](#). All safety assessments/measurements will be listed in by-subject listing.

Subjects will be summarized according to their actual treatment group.

TEAEs will be summarized descriptively overall and by treatment and other safety information will be summarized descriptively by treatment.

All safety analyses will be based on the Safety Set.

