Table 14.2.6.3.7	Subgroup Analysis by Duration of Hemodialysis (Estimand 6) - Difference in Proportions of Subjects with Improvement of SD NRS ≥ 4 from Baseline at Week 4 without Use of Rescue Therapies and without Treatment Discontinuation due to Lack of Efficacy or AE/Death related to the Study Drug - MI under MAR	ITT Set
Table 14.2.6.3.8	Subgroup Analysis by Systemic Anti-Pruritus Treatment (Estimand 6) - Difference in Proportions of Subjects with Improvement of SD NRS ≥ 4 from Baseline at Week 4 without Use of Rescue Therapies and without Treatment Discontinuation due to Lack of Efficacy or AE/Death related to the Study Drug - MI under MAR	ITT Set
Figure 14.2.6.3.9	Forest Plot (Estimand 6) - Difference in Proportions of Subjects achieving an Improvement of SD NRS ≥ 4 from Baseline at Week 4 without Use of Rescue Therapies and without Treatment Discontinuation due to Lack of Efficacy or AE/Death related to the Study Drug - MI under MAR	ITT Set
CCI		
CCI		
Table 14.2.12.1	Summary of Weekly Average of WI NRS - Observed Case	ITT Set
Table 14.2.12.2	ANCOVA of Percent Change from Baseline in Weekly Average of WI NRS at Week 12 - MI under MAR	ITT Set
Table 14.2.12.3	ANCOVA of Percent Change from Baseline in Weekly Average of WI NRS at Week 4 - MI under MAR	ITT Set
CCI		
Table 14.2.14.1	Kaplan-Meier Analysis of Time to Onset of Effect on Pruritus from Baseline	ITT Set
Figure 14.2.14.2	Kaplan-Meier Plots of Time to Onset of Effect on Pruritus from Baseline	ITT Set
Table 14.2.14.3	Competing-Risks Analysis of Time to Onset of Effect on Pruritus from Baseline	ITT Set

TLF	Title	Analysis Set
Figure 14.2.14.4	Competing-Risks Cumulative Incidence Function Plots of Time to Onset of Effect on Pruritus from Baseline	ITT Set
Table 14.2.15.1	Difference in Proportions of Subjects with Improvement of WI NRS ≥ 4 from Baseline at Week 1 without Use of Rescue Therapies - MI under MAR	ITT Set
Table 14.2.16.1	Summary of Investigator's Global Assessment of CKD-aP Skin Status - Observed Case	ITT Set
Table 14.2.16.2	Summary of Proportion of Subjects Achieving IGA Success - Observed Case	ITT Set
Table 14.2.16.3	Difference in Proportions of Subjects achieving IGA Success without Use of Rescue Therapies and without Treatment Discontinuation due to Lack of Efficacy or AE/Death related to the Study Drug - Non-responder imputation	ITT Set
Table 14.3.1.1	Overall Summary of Treatment-Emergent Adverse Events	Safety Set

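### The Week 1 responder analysis leaves drug-related discontinuation and death out of its failure rule, for a reason that does not cover death and without declaring a departure from the protocol

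*SAP*

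**What the plan says.** The rule stands in SAP section 9, in the paragraph on the Week 1 WI NRS responder proportion. That paragraph follows the time-to-onset censoring rules; its own sub-heading is redacted.

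- Rescue users are treatment failures, with later values set to worst and the response set to non-responder.
- On discontinuation and death: "Treatment discontinuation due to lack of efficacy, AE/death related to study drug or any other reason is not a factor at this early timepoint", the reason being "since the second administration is not due until Week 4".
- On missing data, the subject's "binary response will be imputed using MI under MAR assumption".

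Appendix F agrees. Table 14.2.15.1 is titled as improvement "from Baseline at Week 1 without Use of Rescue Therapies - MI under MAR", with no mention of discontinuation or death.

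SAP 4.7 lists the Week 1 endpoint among those to be multiply imputed, but its failure rule does not reach it. Subjects with rescue or drug-related discontinuation "will be considered as treatment failures in the endpoints defined for Estimands 1 to 6", and all six of those are Week 4 or Week 12 endpoints.

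**The concern.** The sentence treats early discontinuation and drug-related death as if they could not bear on Week 1. Both can occur after a single dose. The plan's other responder definitions count them as failures, so the Week 1 rate rests on a looser definition than the Week 4 and Week 12 rates it will be read beside. A subject stopped in Week 1 for a drug-related reaction would be a failure at Weeks 4 and 12 but could be a responder at Week 1. A drug-related death could be scored or imputed as a response.

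At stake is the consistency and face validity of one early-onset result. The primary conclusion is not at stake.

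**Working it through.** **1. Can the event happen in Week 1?**
- Protocol 11.5: "A subject may be withdrawn from the study treatment at any time for the following reasons". The list includes serious immediate-type allergic reactions, which can follow a first injection.
- SAP 8.4.2, on counting missed injections, gives as its example a subject dosed at baseline who stops before Week 4.
- Drug-related death needs no second dose.

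So the event is possible, and the SAP foresees stops before Week 4.

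**2. What happens to such a subject under the Week 1 text?**
SAP section 9 requires at least 4 daily scores in 7 days. SAP Table 4 sets the Week 1 window at Days 1 to 7 for evening entries and Days 2 to 8 for following-morning entries. The window extensions apply only to baseline and Week 12.
- Four or more scores: the observed average is used, and an improvement of at least 4 makes the subject a responder. With evening entries from Day 1, a death on Days 5 to 7 can fall here.
- Fewer than four scores: the response is imputed under MAR. Protocol 19.7 imputes separately by arm from earlier time points, and for Week 1 the only earlier point is baseline.

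Neither route sets the subject to non-responder.

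**3. How do other places treat the same event?**
- Protocol 19.7: treatment failure and non-responder, with no limit by endpoint or week.
- SAP Table 5, the intercurrent events for the study: composite strategy.
- SAP Tables 6 and 7, Estimands 1 to 6: the non-responder definition includes "or use of rescue therapies or treatment discontinuation due to lack of efficacy or AE/death related to study drug".
- SAP section 9, time to onset of a 4-point improvement: a subject who stops for this reason before onset "will be censored and the date of treatment discontinuation will be used as censoring date". The same subject could be censored without onset there and a responder at Week 1.
- SAP section 16: no change to the intent of the protocol.

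Protocol section 19 lets the SAP supersede the protocol where they differ, so the Week 1 wording would govern. SAP section 16 also says that changes will be justified and documented, and this one is not listed.

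**4. How large is the effect?**
The plan states no figure for Week 1. Its only related figure is power of at least 90% at Week 12 with 84 per arm, 20% versus 50%, two-sided alpha 0.025. This reproduces:
- SE under H0 = √(2 × 0.35 × 0.65 / 84) = 0.0736
- SE under Ha = √((0.2 × 0.8 + 0.5 × 0.5) / 84) = 0.0699
- power = Φ((0.30 − 2.241 × 0.0736) / 0.0699) = 97.3%

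The Week 1 rule does not touch it.

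Shift in one arm's Week 1 rate = k × r / 84. Here k is the number of affected subjects and r is the chance that each would otherwise count as a responder. Neither is in the documents. I assume k from 1 to 4. For r I take 1 as the ceiling, and 0.5 and 0.2 borrowed from the Week 12 planning rates.

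| k | r = 1 | r = 0.5 | r = 0.2 |
|---|---|---|---|
| 1 | 1.2 | 0.6 | 0.2 |
| 2 | 2.4 | 1.2 | 0.5 |
| 4 | 4.8 | 2.4 | 1.0 |

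(percentage points)

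**5. Could one subject change the displayed result?**
SAP section 4 flags p-values below 0.025 for all tests. With assumed counts, 84 per arm and an unstratified CMH statistic:
- 13 vs 4 responders: expected 8.5, variance 17 × 151 / (4 × 167) = 3.84, χ² = 4.5² / 3.84 = 5.27, p = 0.0217
- 12 vs 4: expected 8, variance 16 × 152 / (4 × 167) = 3.64, χ² = 4² / 3.64 = 4.39, p = 0.0361
- 19 vs 8 gives 0.0212, and 18 vs 8 gives 0.0334
- 24 vs 12 gives 0.0245, and 23 vs 12 gives 0.0372

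The examples were chosen at the threshold. One reclassified subject changes the flag only when the result is already borderline.

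**The case against.** The best defence is that the SAP has chosen a strategy and said so. At Week 1 the only scheduled dose has been given and no other is due until Week 4, so cancelling later doses cannot alter the exposure behind the Days 1 to 7 scores. Using observed scores after a non-fatal stop is in effect treatment policy, which Table 5 already applies to other discontinuations. The paragraph, SAP 4.7 and the table title agree with one another. This stands for non-fatal stops as a defensible choice. It does not stand as drafting: no strategy is named, the departure from Protocol 19.7 is not declared, and the reason says nothing about drug-related death.

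Redaction also limits certainty. SAP 9.2.1 names Estimands 2, 3 and 5 as sharing the primary imputation dataset, in which worst values are already set, and is then cut off. Appendix C is hidden. If Week 1 is drawn from that dataset, some of these subjects may already carry worst values. But the explicit Week 1 sentence points the other way, so the wording would still need reconciling.

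A reader might infer more than the documents support:
- *Every drug-related death before Day 8 is imputed.* Only if fewer than four daily scores exist.
- *The same reason would exempt Week 4.* Not cleanly. The Week 4 visit is Day 29 ± 3, so the second injection can fall from Day 26, inside the Days 22 to 28 evening window. At Week 1 no such overlap is possible.
- *The bias favours nemolizumab.* No first-week drug-related discontinuation rate is given for any arm. Relatedness is judged blinded for nemolizumab or placebo, and the visible phase 2a summary reports no clinically significant safety findings in the nemolizumab groups.

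**Conclusion.** The point holds as a minor inconsistency. The Week 1 failure rule leaves out drug-related discontinuation and death, on a reason that cannot cover death, and differs from Protocol 19.7 and SAP Table 5 without being declared.

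The size is at most 1.2 percentage points in one arm per affected subject, and nothing if that subject would have been a non-responder anyway. The larger values in the table are ceilings under assumed counts, not estimates. The direction of any net effect is unknown. The endpoint is not in the primary and key secondary sequence of SAP 4.4, so confirmatory type I error, power and the primary conclusion are unaffected.

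The verdict rests on the visible text and assumes that the redacted appendix does not override the explicit sentence.

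**What to change.** - Delete the sentence declaring discontinuation and death irrelevant at Week 1.
- State that subjects who use rescue, or who discontinue for lack of efficacy or for an AE or death related to study drug, on or before the end of the Week 1 window are Week 1 non-responders under the Table 5 composite rule. Give the cut-off day, since Table 4 ends the evening window on Day 7 and the morning windows on Day 8.
- Extend the failure rule in SAP 4.7 to the Week 1 endpoint, and change the title of Table 14.2.15.1 to match.
- If treatment policy is intended for non-fatal stops, name it in the Week 1 paragraph, give the exposure argument as its justification, and list it in SAP section 16 as a departure from Protocol 19.7. Drug-related death should be a non-responder in either case.

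The cost is one sentence, one clause and one table title. Discontinuation date and reason are already needed for Estimands 1 to 6 and for time-to-onset censoring, so no new data are required. Sample size and alpha do not change.

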All other opioids (e.g. codeine, tramadol, oxycodone, hydrocodone, methadone, buprenorphine)	Stable dose for 2 weeks	Stable dose
Change in hemodialysis treatment (i.e., number of hemodialysis sessions per week, change in dialyzer or switch between hemodialysis and hemodiafiltration). Also see in inclusion # 2	Not allowed for 8 weeks	Prohibited
Live attenuated vaccine and non-live vaccine (Seasonal vaccine (e.g., influenza), emergency vaccine (e.g., rabies or tetanus) and COVID vaccines as noted in Section 12.5.2 are permitted)	Not allowed for 4 weeks	Prohibited

Abbreviations: PDE-4 = phosphodiesterase-4; TCI = topical calcineurin inhibitor; TCS = topical corticosteroid.

For medications given as needed (“PRN”), stable dose during the study is defined as that without an increase or decrease by $\geq 75\%$ in the total weekly dose relative to the dose during the last week of screening. For example, if the total weekly dose of 100 mg of diphenhydramine during the last week of the screening period increased to 175 mg in a given week during the study, this would be considered not a stable dose. During the screening period, a “stable dose” is one that has not changed (increase or decrease) by $\geq 75\%$ during the period of required stability.

Note: Subjects should not interrupt ongoing treatment with medications important for the subject’s health for the sole purpose of participating in this study.

20. Requiring rescue therapy for pruritus during the screening period or expected to require rescue therapy within 4 weeks following the baseline visit. Section 12.5.1.2.
21. Previous treatment with nemolizumab.

22. History of hypersensitivity (including anaphylaxis) to an immunoglobulin product (plasma-derived or recombinant, e.g. monoclonal antibody) or to any of the study drug excipients.
23. Currently participating or participated in any other study of an investigational drug or device, within the past four weeks (or five half-lives of the investigational medication, whichever is longer) before the screening visit.
24. History of alcohol or substance abuse within six months of the screening visit.

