19.5 Pharmacokinetic and Anti-drug Antibody Analysis

Descriptive statistics (arithmetic and geometric mean, standard deviation [SD], coefficient of variation [CV%], median, first quartile, third quartile, minimum [min.], maximum [max.]) will be used to summarize the observed nemolizumab C_{trough} in serum.

In addition, individual and mean serum concentration versus time curves will be presented for both linear and semi-log scales. Treatment related positive ADA subjects and positive ADA subject will be identified in the graphs.

Descriptive statistics (n, arithmetic mean, standard deviation, Coefficient of Variation (CV)%, geometric mean, minimum, median, maximum) will be calculated for all individual derived parameters.

Incidence of positive ADA results will be summarized (absolute occurrence, percent of subjects, and treatment-related ADA). The ADA results presentation will be detailed in the SAP.

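### The SAP 11 definition of treatment-related ADA has no boosted category, so a subject confirmed positive at baseline whose titer rises on treatment cannot be counted in it

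*SAP*

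**What the plan says.** SAP 11 (Immunogenicity Analyses) names immunogenicity as an endpoint and lists four kinds of assay result: "screening, confirmatory, titer, Nab". It then plans the incidence output: "incidence of positive ADA results (absolute occurrence, percent of subject, and treatment-related ADA) will be summarized by visit and by treatment group". The definition follows: "A treatment-related ADA is defined when at baseline, the screening or confirmatory ADA result is negative, and the post-baseline confirmatory ADA result is positive". A by-subject listing is also planned; Appendix F of the SAP gives it as Listing 16.2.5.3.

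Protocol 19.5 plans the same incidence outputs without defining the treatment-related category in its visible text. It leaves the detail to the SAP: "The ADA results presentation will be detailed in the SAP". On the concentration-time curves it says: "Treatment related positive ADA subjects and positive ADA subject will be identified in the graphs". Protocol 19 states that the SAP prevails where the two documents differ, so SAP 11 is the operative text. Its definition is not redacted.

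**The concern.** A drug can provoke antibodies in someone who had none, or raise antibodies that were already there. The SAP rule recognises only the first. The titer result that would show the second is collected and summarized in the same paragraph, but it plays no part in classifying subjects.

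Treatment-related ADA is the only ADA output that attributes a response to study drug, and it is shown by treatment group. If boosted responses are left out, the category does not cover everything its name suggests. On the concentration graphs a boosted subject would also carry the same mark as one whose pre-existing reactivity never changed. Elsewhere the protocol treats worsening as attributable in time: its definition of treatment-emergent adverse events (Protocol 19.4.2) includes events that worsen after the first administration. The ADA rule has no counterpart.

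**Working it through.** **No planned figure to reproduce.** The documents state no ADA rate, titer threshold or ADA sample size. The check is therefore on the logic of the rule, followed by an illustration of size under stated assumptions.

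**Case check of the SAP 11 rule**

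| Baseline | After baseline | Treatment-related under SAP 11? |
|---|---|---|
| Screening negative | Confirmed positive | Yes |
| Screening positive, confirmatory negative | Confirmed positive | Yes |
| Confirmed positive, titer stable | Confirmed positive | No (appropriate) |
| Confirmed positive, titer rises | Confirmed positive | No, whatever the rise |
| No baseline result | Confirmed positive | Not addressed; the negative-baseline condition is not shown to be met |

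So the treatment-related count contains no boosted subject. It falls short of induced plus boosted by exactly the number boosted, and the shortfall is zero if nobody is boosted.

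**Inputs for the illustration**

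- n = 84 per arm, so 2 × 84 = 168 on nemolizumab (SAP 4.2).
- p = share confirmed positive at baseline. Not in the documents; assumed 0 to 10%.
- b = share of those who are boosted. Not in the documents; assumed 10 to 50%.
- i = share of baseline negatives who convert. Not in the documents; assumed 5% for one example.
- Protocol 11.3, criterion 21, excludes "Previous treatment with nemolizumab", so any baseline positive would be a natural or cross-reactive antibody. That argues for low values of p.

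**Subjects omitted per arm = n × p × b**

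| p | b = 10% | b = 50% |
|---|---|---|
| 0% | 0 | 0 |
| 2% | 84 × 0.02 × 0.10 = 0.2 | 84 × 0.02 × 0.50 = 0.8 |
| 5% | 84 × 0.05 × 0.10 = 0.4 | 84 × 0.05 × 0.50 = 2.1 |
| 10% | 84 × 0.10 × 0.10 = 0.8 | 84 × 0.10 × 0.50 = 4.2 |

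**One worked rate**, with p = 5%, b = 30%, i = 5%:

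- Counted under SAP 11: 84 × 0.95 × 0.05 = 3.99, and 3.99 / 84 = 4.75%.
- Boosted, not counted: 84 × 0.05 × 0.30 = 1.26, and 1.26 / 84 = 1.50%.
- Total with a boosted category: 4.75% + 1.50% = 6.25%.

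**Could the case arise at all?** The chance of at least one baseline positive among 168 is 1 − (1 − p)^168. For p = 1% this is 1 − 0.99^168 = 0.815; for p = 2% it is 0.966; for p = 5% or 10% it exceeds 0.99. That is the chance that a subject falls outside the rule's reach, not the chance that anyone is boosted.

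**The case against.** The strongest reply is that little is hidden. Four parts of it stand.

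- **Boosting remains visible in the data.** Titers are summarized by visit and group, and Listing 16.2.5.3 shows each subject's results. A reader might infer that boosted subjects cannot be told apart from stable ones anywhere. The documents do not support that: a rise can be read from the listing. What is missing is a label and a count.
- **The graphs do not call these subjects unrelated.** Protocol 19.5 marks ADA-positive subjects as well as treatment-related ones, so a boosted subject still carries a mark. Nor does any visible text say that the graphs serve to judge whether ADA lowers exposure.
- **The rule can also err upwards.** It requires neither persistence nor a minimum titer, so one transient conversion counts as treatment-related. A reader might infer that the reported rate is biased downwards overall. That does not follow; only the omission of boosted responses is established.
- **The size is assumed.** Prior nemolizumab is excluded, and so is a history of hypersensitivity to immunoglobulin products (criterion 22). The number omitted may be zero.

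On a missing baseline, SAP 4 takes the last non-missing value before the first injection, which limits how often this occurs. Counting such subjects as treatment-induced could label unrecognised pre-existing antibodies as drug-induced, which is the opposite error.

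Protocol section 18, including 18.1 on ADA, is redacted and may hold more. But SAP 11 is readable, is the operative text, and contains no titer-rise branch. None of these replies supplies a boosted category.

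**Conclusion.** The point holds in a limited form. As written, the treatment-related category covers treatment-induced responses only. A subject confirmed positive at baseline cannot enter it, whatever the titer does, and the planned incidence table and graph flag do not separate boosted from stable pre-existing reactivity.

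The case logic rests on the SAP text alone. The size does not: 0 to 4.2 subjects per arm depends wholly on the assumed prevalence and boosting share, and zero is a real possibility. It would be wrong to conclude that a known number of cases will be lost.

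It would also be wrong to read this as a threat to the efficacy conclusions. Immunogenicity is summarized descriptively, lies outside the testing sequence in SAP 4.4 and enters none of the efficacy estimands. The reason to act is that the correction is cheap and the threshold for a rise should be fixed before treatment codes are known. A cut-off picked later from the listing would be post hoc.

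**What to change.** Amend SAP 11 before unblinding:

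1. Keep the present definition and name it treatment-induced ADA.
2. Add treatment-boosted ADA: confirmed positive at baseline, with a post-baseline titer rise above a pre-specified threshold. Take the threshold from the assay's validated titer variability and state it in the SAP. The documents give no value, so none is proposed here.
3. Report induced, boosted and their total by arm. Include placebo, where apparent rises show background variation.
4. Use the total for the treatment-related flag on the concentration graphs.
5. Show subjects with no baseline result and a confirmed positive result afterwards on a separate line, outside the induced count.

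Cost: SAP wording and two or three extra table rows, with no new samples or assays. The reported treatment-related rate may be slightly higher. Because the induced row is unchanged, the figure under the present definition stays visible.
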